Drug Interactions*	
Anti-arrhythmic drugs, tricyclic anti-depressants, anti-psychotics, chloroquine & hydroxychloroquine, some other TB drugs (e.g. clofazimine & fluoroquinolones), and macrolide antibiotics may increase risk of QTc prolongation.
 
CYP3A4 inducers (including rifampicin, rifabutin, rifapentine, phenytoin and carbamazepine) can accelerate metabolism of bedaquiline resulting in reduced effect.
 
CYP3A4 inhibitors (including azole antifungals) slow metabolism of bedaquiline resulting in increased concentrations of bedaquiline.
 
Some anti-retroviral drugs are CYP3A4 inducers (e.g. efavirenz) or inhibitors (e.g. the protease inhibitors), so combined HIV and TB therapy requires careful consideration.

Guidance on monitoring	
ECG: before initiation of treatment, and at least 2, 4, 8, 12 and 24 weeks after starting treatment. More frequently if heart conditions, hypothyroidism or electrolyte disturbances are present.
 
LFT: at baseline and repeated monthly.

Pretomanid	
Activity against TB	Indicated as part of a combination regimen with bedaquiline and linezolid for treatment of adults with pulmonary XDR or treatment-intolerant or nonresponsive MDR TB
Dose	Pretomanid 200 mg daily 26 weeks
Special Circumstances	
Use in renal or hepatic disease: Effect on the safety, effectiveness, and pharmacokinetics unknown.
 
If hepatotoxicity develops on a pretomanid-containing regimen, the entire regimen should be interrupted if:
 
 • Any aminotransferase elevation is accompanied by a total bilirubin elevation $>2x$ ULN • Aminotransferase elevations are $>8 \times$ ULN • Aminotransferase elevations are $>5x$ ULN and persist beyond 2 weeks 
Any concerns about hepatotoxicity should be discussed promptly with the Medical Monitoring team.
 
There are no data on the use of pretomanid in pregnancy, or during breast feeding.

Adverse Reactions*	
In clinical trials of the bedaquiline-pretomanid-linezolid regimen, reported severe adverse reactions have included:
 
 • hepatotoxicity • myelosuppression, peripheral and optic neuropathy (all known adverse reactions to linezolid)

	
 QTc prolongation (known adverse reaction to bedaquiline) 
Pre-clinical animal studies reported testicular atrophy and fertility problems. Potential effects on human male fertility are still being evaluated.

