Contraindications	
Pretomanid should always be initiated as part of a treatment regimen including bedaquiline and linezolid, so it is contraindicated if these drugs are contra-indicated.
 
After treatment initiation: If bedaquiline is discontinued, pretomanid must also be discontinued, and the entire regimen should be re-assessed.
 
If linezolid is permanently discontinued during the initial four consecutive weeks of treatment, the bedaquiline-pretomanid-linezolid regimen should also be discontinued and the entire treatment regimen should be re-assessed.
 
If linezolid is discontinued after the initial four weeks of consecutive treatment, the bedaquiline-pretomanid regimen may be continued.

Drug Interactions*	
CYP3A4 Inducers: Co-administration of pretomanid with rifampicin and efavirenz may result in a decrease in pretomanid plasma concentrations. Avoid co-administration of the combination bedaquiline-pretomanid-linezolid regimen with rifampin, efavirenz, or other strong or moderate CYP3A4 inducers.
 
Lopinavir/ritonavir (LPV/r): Co-administration of pretomanid with LPV/r did not affect the plasma concentrations of pretomanid. LPV/r can be co-administered with the combination bedaquiline-pretomanid-linezolid regimen.

Guidance on monitoring	
ECG before initiation of treatment.
 
Check serum potassium, calcium and magnesium and correct abnormalities before initiation of treatment.
 
Assess for symptoms and signs of liver disease (such as fatigue, anorexia, nausea, jaundice, dark urine, liver tenderness, and hepatomegaly and check LFTs (alanine aminotransferase [ALT], aspartate aminotransferase [AST], alkaline phosphatase, and bilirubin) before initiation of treatment.
 
Monitor clinically and biochemically for hepatotoxicity during treatment.

Linezolid	
Activity against TB, Mechanism of action, and metabolism	Bactericidal: Inhibits protein synthesis.

Dose	Adults: 600 mg, once daily. (Reduce to 300 mg/day if serious adverse effects develop). Ongoing trials may inform on revised dosing. Vitamin B6: All participants should receive vitamin B6 while receiving linezolid.
Special Circumstances	Use in renal disease: No dose adjustment is recommended, but metabolites may accumulate. Use in hepatic disease: Rarely associated with increased transaminases. Use in pregnancy/breastfeeding: Not recommended during pregnancy or breastfeeding due to limited data.

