Audiometry	Perform wherever possible if planning to initiation injectable second line TB drugs (aminoglycosides or capreomycin); however, preferably avoid these drugs, esp. if there is any baseline abnormality

*Discuss points of concern with Medical Monitoring Team.

2. Safety monitoring during DR-TB treatment

Monitoring evaluation	Recommended frequency*
Routine Laboratory measurements as per in-country guideline	
Renal function (esp. serum potassium and creatinine)	At baseline, then monthly if possible while receiving an injectable agent Consider more frequently in higher risk groups (e.g. HIV-infected participants, diabetics, known underlying renal disease)
Serum magnesium and calcium	Check, if possible, when hypokalaemia is diagnosed Repeat check potassium, magnesium, calcium if QTc prolongation or cardiac arrhythmias
Liver function (bilirubin, ALT)	Check monthly on rifampicin, isoniazid, pyrazinamide, bedaquiline and pretomanid containing regimens Frequency may be gradually reduced if stable, or may be more frequent in high-risk groups (e.g. underlying liver disease, viral hepatitis)
Full blood count	If on linezolid, check weekly at first then monthly (may reduce frequency in longer-term use if stable)
TSH	Check every 3 months if receiving both ethionamide/prothionamide and PAS Check every six months if receiving one of ethionamide/prothionamide or PAS Also monitor for clinical signs of hypothyroidism if using those drugs
Lactic acid	Check if concern of lactic acidosis on linezolid and / or antiretroviral therapy
Additional considerations	
Visual, neurological and psychological evaluations	Perform according to clinical concern at each consultation
ECG	Repeat during treatment; frequency dependent on specific QTc prolonging drugs in treatment regimen, and other cardiac risk factors
Audiometry	Repeat monthly, if possible, whilst on second-line injectable drugs

***Discuss emergent abnormalities with Medical Monitoring Team (consider: is there a need for symptomatic therapy, dose change, treatment interruption, or change of regimen?).**

3. Initial management of common adverse events

Adverse events should be reported according to Sections 10.1 – 10.3 of the protocol. The table below provides additional information but is not exhaustive. Support should be sought from the Medical Monitoring Team as necessary.

Adverse event	Likely drug	Initial management	Comment

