Rash / allergy / anaphylaxis	Any drug	
If serious reaction, stop therapy and manage according to emergency protocols
 
Eliminate other potential allergens
 
Minor dermatological reactions may be treated with antihistamines and topical/systemic corticosteroids
	
Dry skin and chronic skin discolouration are common, sometimes problematic, side-effects of clofazimine
 
Re-introduction of drugs should be discussed with the PI and Medical Monitoring Team; any drug causing anaphylaxis or Stevens-Johnson-Syndrome should never be reintroduced
 
All allergies should be noted on the CRF and in the participant's medical record

Nausea / vomiting / diarrhoea / abdominal pain	Any drug, esp. Ethionamide / Prothionamide, PAS	
Symptomatic therapy including hydration and anti-emetics
 
Investigate potential causes including the risk of underlying systemic toxicity (e.g. lactic acidosis, liver dysfunction)
 
Check electrolytes, especially if using QTc prolonging medications
 
Consider adjusting timings / doses of suspected drugs
	
Temporarily suspending suspect drugs may be necessary
 
Some anti-emetic drugs (e.g. ondansetron) can also prolong the QTc; be cautious monitor closely if concurrently using QTc prolonging anti-TB medications
 
Antacids may interfere with absorption of fluoroquinolones; avoid concurrent use

Adverse event	Likely drug	Initial management	Comment
Hepatotoxicity	Rifampicin, isoniazid, pyrazinamide, bedaquiline, pretomanid	
Stop treatment if
 
 Any ALT elevation is accompanied by a bilirubin elevation $>2 \times$ ULN ALT is $>8 \times$ ULN ALT is $>5 \times$ ULN and persist beyond 2 weeks 	
Eliminate other potential causes of liver toxicity (e.g. viral hepatitis, alcohol, concurrent medications)
 
Re-introduction of drugs, after interruption, should be discussed with the PI and Medical Monitoring Team

		Continue to monitor liver function until it returns to normal; seek specialist support for progressive disease	
Hypothyroidism	Ethionamide / prothionamide, PAS	Can be treated with levothyroxine and TSH monitoring	Usually completely reversible on completion of therapy.

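### For pretomanid-containing regimens, the hepatotoxicity triggers are written for any aminotransferase in Table 9 but for ALT only in Appendix I, and no section names AST for on-treatment testing

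*Protocol*

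**What the plan says.** **Section 10.4, Table 9, pretomanid, special circumstances.** The rule opens "If hepatotoxicity develops on a pretomanid-containing regimen, the entire regimen should be interrupted if" and lists three conditions. The first is "Any aminotransferase elevation is accompanied by a total bilirubin elevation" of more than 2 × ULN. The other two both begin "Aminotransferase elevations are": one is above 8 × ULN, the other above 5 × ULN and lasting more than 2 weeks. Any hepatotoxicity concern is to be taken promptly to the Medical Monitoring Team.

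**Section 10.4, Table 9, pretomanid, monitoring.** Before treatment, sites "check LFTs (alanine aminotransferase [ALT], aspartate aminotransferase [AST], alkaline phosphatase, and bilirubin) before initiation of treatment". During treatment, clinical and biochemical monitoring is asked for, with no analyte and no interval.

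**Section 10.4, Table 9, bedaquiline, monitoring.** Liver function tests are required at baseline and monthly; the analytes are not listed in that row.

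**Appendix I, part 2 (monitoring during treatment).** The row is "Liver function (bilirubin, ALT"), with the instruction "Check monthly on rifampicin, isoniazid, pyrazinamide, bedaquiline and pretomanid containing regimens".

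**Appendix I, part 3 (hepatotoxicity).** The drugs are "Rifampicin, isoniazid, pyrazinamide, bedaquiline, pretomanid". Treatment is stopped if "Any ALT elevation is accompanied by a bilirubin elevation" of more than 2 × ULN, if ALT exceeds 8 × ULN, or if ALT exceeds 5 × ULN beyond 2 weeks.

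**Status of the two texts.** Appendix I calls itself a general guide that supplements section 10.4. Section 10.4 in turn sends clinicians to Appendix I for medical management.

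**The concern.** The two places give what is evidently the same rule, with the same cut-offs, but apply it to different laboratory values. A clinician on a site treating with bedaquiline, pretomanid and linezolid (BPaL) could consult either page. When AST and ALT fall on different sides of a cut-off, one page states an interruption trigger and the other does not.

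The monitoring text adds to this. The Table 9 rule can act on AST only if AST is measured during treatment, yet no section asks for it by name after the pre-treatment check.

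What is at stake is uniform handling of a safety rule across 13 sites in three countries. Section 12.2 makes consistent clinical management a purpose of the Medical Monitoring Team, Table 2 proposes BPaL in two of its rows, and Table 9 lists hepatotoxicity among the severe reactions reported with that regimen. Stopping a drug or regimen for safety is a secondary objective in section 4.4.1, so an ambiguous interruption rule touches something the study means to describe.

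**Working it through.** No formula applies and the plan states no figure to reproduce. The check is a line-by-line comparison.

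**Step 1: triggers side by side (pretomanid-containing regimens).**

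| Trigger | Table 9 | Appendix I, part 3 | Cut-off | Analyte |
|---|---|---|---|---|
| 1 | Any aminotransferase raised, with total bilirubin > 2 × ULN | ALT raised, with bilirubin > 2 × ULN | Same | Differs |
| 2 | Aminotransferase > 8 × ULN | ALT > 8 × ULN | Same | Differs |
| 3 | Aminotransferase > 5 × ULN beyond 2 weeks | ALT > 5 × ULN beyond 2 weeks | Same | Differs |

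The cut-offs agree on 3 of 3 lines and the analyte differs on 3 of 3.

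**Step 2: direction of the disagreement.** ALT is an aminotransferase, so every case that meets an Appendix I trigger also meets the matching Table 9 trigger. The reverse fails exactly when AST meets the condition and ALT does not. The disagreement therefore runs one way: Table 9 triggers and Appendix I does not.

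**Step 3: a worked case.** Take AST 9 × ULN, ALT 4 × ULN and normal bilirubin on BPaL.
- Table 9, trigger 2: 9 > 8, so it is met.
- Appendix I, trigger 1: bilirubin is normal, so not met. Trigger 2: 4 is below 8, not met. Trigger 3: 4 is below 5, not met.

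Table 9 says interrupt the entire regimen. Appendix I states no stop trigger for this case, but its footnote to part 2 sends emergent abnormalities to the Medical Monitoring Team, with treatment interruption among the options to consider.

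**Step 4: is AST available on treatment?**

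| Place | What it asks for | AST named? |
|---|---|---|
| Table 9, pretomanid, before treatment | ALT, AST, alkaline phosphatase, bilirubin | Yes |
| Table 9, pretomanid, during treatment | Biochemical monitoring | No |
| Table 9, bedaquiline | Liver function tests at baseline and monthly | No |
| Table 3, note e (laboratory safety) | Clinical chemistry by in-country standard of care | No |
| Appendix I, part 1 (baseline) | Liver function, especially bilirubin and ALT | No |
| Appendix I, part 2 (monthly) | Bilirubin and ALT | No |

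AST is named in one of six places, and that one is before treatment. During treatment it is neither required by name nor excluded.

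**The case against.** The strongest reply is that the texts are nested rather than opposed. Appendix I supplements section 10.4, says its adverse-event table is not exhaustive, and nowhere tells a site to continue when AST is high. Read together, the wider Table 9 rule still governs pretomanid regimens. This stands in part: Table 9 is not cancelled. But section 10.4 itself directs clinicians to Appendix I for management, Appendix I restates the rule with the same numbers and a narrower analyte, and nothing there says that the wider wording prevails.

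A second reply is that AST will be measured anyway. BPaL contains bedaquiline, for which Table 9 wants monthly liver function tests, and the pretomanid row of the same table lists AST among such tests. Local chemistry panels may include it too. This is a fair reading and it limits the finding. A reader might infer that AST-led liver injury would go undetected, or that AST would not be measured after baseline; the protocol does not support either, since on-treatment AST is left open. Even where AST is reported, though, the two rules still differ on whether it counts.

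A reader might also infer that Appendix I leads to no action. It does not: emergent abnormalities go to the Medical Monitoring Team, as do hepatotoxicity concerns under Table 9.

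Finally, a reader might infer that secondary outcomes are affected. Section 4.5 lists the incidence of adverse drug reactions, but neither a hepatic outcome nor discontinuation; discontinuation for safety appears only as an objective in section 4.4.1. The disputed lines concern interruption, and adverse events are recorded by clinical grade under section 10.1, not by these triggers. Any effect on reported rates is speculative.

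**Conclusion.** The inconsistency is real and minor. For pretomanid-containing regimens, all three triggers share a cut-off and differ in analyte between Table 9 and Appendix I. The Table 9 rule also depends on a value that no section requires by name during treatment. The result is one class of case, AST beyond a threshold with ALT below it, that is a stated interruption trigger in one place and a matter for discussion in the other.

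The conclusion rests on two readings: that aminotransferase in Table 9 covers both AST and ALT, which its own pre-treatment list supports, and that the Appendix I row applies to pretomanid, which it names. It does not extend to regimens without pretomanid, for which Table 9 has no such rule and Appendix I stands alone. How often AST leads ALT is not in the document, so the number of participants affected cannot be estimated. Nothing here bears on the primary outcomes or the sample size, and this review takes no position on which wording is clinically right.

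**What to change.** Reconcile the pretomanid rows of Table 9 (special circumstances and monitoring) with the liver rows in parts 1, 2 and 3 of Appendix I, so that the same analytes are monitored on treatment and enter the same rule. Alternatively, add a sentence saying which text prevails for pretomanid-containing regimens, and make the on-treatment monitoring list match the rule that prevails. The clinical leads and the Medical Monitoring Team decide which analytes.

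The cost is a wording change in a protocol amendment. If AST is kept in the rule, it can be read from the blood sample already drawn for the other liver tests, so no extra visit or draw is needed.

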in a single-arm randomized controlled trial which demonstrated that 90% of patients recorded a favourable treatment outcome. Treatment associated toxicity linked to the use of linezolid within the regimen was reported as manageable with dose reduction and interruption of linezolid use (16). The BPaL regimen recently received Food And Drug Administration (FDA) approval for use in people with DR-TB or treatment-intolerant/non-responsive MDR-TB or patients for whom there is no other viable as per WHO recommendations (17).

Another novel, short-course regimen under evaluation is the BPaMZ regimen indicated for use in HR-TB, RR-TB and MDR-TB is currently in late-stage clinical development. The regimen incorporates the use of two novel drugs, BDQ and pretomanid, in combination with pyrazinamide and moxifloxacin (SimpliciTB study). Pre-clinical data in a murine model demonstrated potent sterilising activity (18). Phase 2B human study data indicates superior efficacy of the novel combination in patients with DS-TB and MDR-TB (19). A phase 3 trial of the BPaMZ regimen (SimpliciTB; NCT03338621) is currently evaluating the potential to both shorten treatment to 4 months for patients with DS-TB and also effectively treat patients with RR- or MDR-TB (as a 6-month regimen, because of the higher risk of associated resistance to pyrazinamide) (20). Modelling analysis on the projected patient outcomes using the BPaMZ regimens indicates that universal implementation of the regimen has the potential to increase the percentage of patients with RR-TB who are cured from 60% to nearly 90% and maintain nearly 90% cure among patients with DS-TB. Further, the regimen could reduce treatment duration by two months and reduce infectious person-time by 50% (RR-TB) (21).

The current programmatic DR-TB treatment regimens for each country and the proposed novel interventions are described in Table 2. Novel DR-TB regimens under evaluation will be considered for inclusion by the TRiAD Joint Steering Committee (JSC) once sufficient safety and efficacy data becomes available.

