5. STUDY INTERVENTION

There are 3 study interventions:

1. The Xpert MTB/XDR assay will be used as a diagnostic adjunct to any currently available Nucleic Acid Amplification Tests for drug-resistance detection changes to screen participants. The Xpert MTB/XDR assay will enable prompt identification of the following DR-TB participant categories:
 - a. HR-TB
 - b. Rif mono-resistant TB
 - c. MDR-TB
 - d. Additional fluoroquinolone (FQ) resistance, i.e., pre- XDR TB
2. Early initiation of the most appropriate, evidence-based DR-TB regimen. This will be guided by the TB resistance pattern categorization from the Xpert MTB/XDR diagnostic.

Choice of DR- TB regimen will be determined by:

- a. Best available evidence generated from use of novel regimens as they become available, or
 - b. Current WHO and in-country guidelines (Table 2).
3. In parallel, the TB-MBLA will be used to provide real-time bacillary load monitoring over the course of treatment to assess response to treatment.

Table 2: Current Drug-Resistant TB Treatment Regimen by TB resistance profile and proposed study approach

Current Guidelines on DR- TB treatment	Regimen class	Current Recommended Regimen with Duration (months) by Drug resistance profile per participating country	Proposed All-oral regimen [#]
	HR-TB	RHZE + Lfx (6)	RHZE + Lfx (6) [#]
RR-TB and MDR-TB Short- Course Regimen		
All oral regimen:
 
SA: (4-6)BDQ-Lfx (or MXF)- LZD, INHhd-CFZ-E-Z/ (5) LFX-CFZ-E-Z Nigeria: (4-6)BDQ-MFX-HH-PTO-CFZ-E-Z/ (5)BDQ (2) MFX-CFZ-E-Z Ethiopia:(4-6)AM-MFX-CFZ-HH-PTO-E-Z/ (5)MFX-CFZ-E-Z
 
or
 
Injection-based regimen:
 
(4)AMK-MFX-CFZ- INHhd -PTO-E-Z/(5) MFX-CFZ-E-Z
	BDQ based all-oral regimen [#]
RR-TB; MDR-TB; and PreXDR-TB (Second-line resistance) Long all-oral Regimen* :		
SA: (6)BDQ-LFX-CFZ-LZD/(12)LFX-CFZ- LZD Nigeria: (6)BDQ-MFX-CFZ-LZD/ (12) MFX- CFZ-LZD Ethiopia: (6) BDQ-LFX-LZD-CFZ-CS/(14) LFX- LZD-CFZ-CS
	BPaL [#]
PreXDR-TB (FQ resistance) and XDR-TB# Long Individualised Regimen*:		
SA: (6-8)BDQ-CFZ-LZD-DLM-TRD/(12)CFZ-LZD-TRD-Z- INHhd Nigeria: (6)BDQ-CFZ-LZD-CS/ (12)CFZ-LZD- CS Ethiopia: (BDQ)-(LFX)- (MFX)-(LZD)-(CFZ)-(CS)- (DLM)-(PTO)-(Z)-(AM)-(S)-(PAS)
	BPaL [#]

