Adverse Reactions*	Common: diarrhoea, nausea, vomiting, headache, transient increases in LFTs. Serious: myelosuppression (decreased level of platelets, white blood cells, and/or anaemia), optic and peripheral neuropathy (increased risk with prolonged treatment and may be irreversible) lactic acidosis (may present recurrent nausea or vomiting, unexplained acidosis, or a low bicarbonate level).
Contraindications	Hypersensitivity to oxazolidinones. Symptoms of neuropathy (pain, numbness, tingling or weakness in the extremities).
Drug Interactions*	Avoid concurrent use with serotonergic agents, such as monoamine oxidase inhibitors (MAOIs), selective serotonin reuptake inhibitors (e.g. fluoxetine, paroxetine), lithium, tricyclic antidepressants etc., as it may cause serious neurological reactions such as seizures and serotonin syndrome.
Guidance on monitoring	Monitor for peripheral neuropathy and optic neuritis (visual eye tests every two months or if symptoms develop, clinical examination for peripheral neuropathy monthly or if symptoms develop). Monitor a complete blood count weekly during the initial period, then monthly.
Moxifloxacin	
Activity against TB, Mechanism of action, and metabolism	Bactericidal: inhibits DNA gyrase
Dose	Adults: 400 mg daily (oral or IV)
Special Circumstances	Use in renal disease: Excretion unchanged during renal failure; no data on effect of dialysis. Use in hepatic disease: Rarely associated with hepatotoxicity; use with caution. No dose adjustment required for mild or moderate liver disease. Use during pregnancy/breastfeeding: Fluoroquinolones are generally avoided during pregnancy and breastfeeding due to observation of arthropathy in animal models. However, there are

	case reports of fluoroquinolones being used safely during pregnancy.
Adverse Reactions*	Common: Nausea, vomiting, diarrhoea, dizziness, headache, transient increases in LFTs. Serious: QTc prolongation (more common in hypokalaemia, predisposing cardiac conditions, or if combined with other QTc prolonging drugs), arthralgia, tendon inflammation and/or rupture, hepatotoxicity, hypo/hyperglycaemia.
Contraindications	Fluoroquinolone intolerance, prolonged QTc (>500ms). Fluoroquinolones may lower seizure threshold, so use with caution in participants with CNS disorders.
Drug Interactions*	Caution if used alongside other drugs known to prolong QTc.

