Arthralgia	Pyrazinamide / fluoroquinolones, bedaquiline	Check urate, treat with non-steroidal anti-inflammatory drugs if possible Consider dose reduction or interruption of suspect drug, if symptoms are severe	Rarely, severe tendonitis and tendon rupture can occur with fluoroquinolones; should significant tendon inflammation be suspected consider stopping the fluoroquinolone
Nephrotoxicity	Injectable second line drugs	Monitor renal function and serum electrolytes closely Consider reducing to thrice weekly dosing or changing to an all-oral treatment regimen if possible	First-line recommendations for DR-TB now avoid nephrotoxic injectable drugs whenever possible
Deafness / vestibular toxicity (dizziness and tinnitus)	Injectable second line drugs	Consider reducing to thrice weekly dosing or changing to an all-oral treatment regimen if possible	Hearing loss from injectable drugs can be permanent: first-line recommendations for DR-TB now avoid nephrotoxic injectable drugs whenever possible

Adverse event	Likely drug	Initial management	Comment
Peripheral neuropathy	Cycloserine / terizidone, linezolid, isoniazid	Correct any vitamin or nutritional deficiencies. Increase pyridoxine to the maximum daily dose (200mg /day) Simple and neuropathic analgesia Consider whether drug doses can be reduced without compromising the regimen. Switching potential culprit drugs to alternatives may be necessary	Be mindful of other potential contributors to multi-factorial neuropathy (e.g. HIV, ART, diabetes, hypothyroidism, alcohol)
Psychological upset (depression / psychosis)	Cycloserine / terizidone	Dose reduction or stopping the drug may be necessary.	Consider all potential contributors to psychological problems

			– seek specialist support as appropriate
Visual disturbance / optic neuritis	Ethambutol / linezolid	Stop suspect drug Seek ophthalmology support	Ethambutol is typically associated with colour blindness
Lactic acidosis	Linezolid	Stop linezolid	Consider other potential causes of lactic acidosis (e.g. ART, sepsis)

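### The Table 9 linezolid dose row offers only dose reduction for serious adverse effects, while Appendix I directs a stop for lactic acidosis and, less directly, for optic neuritis, and the protocol does not say which prevails

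*Protocol*

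**What the plan says.** Protocol Section 10.4, Table 9, sets the adult linezolid dose at 600 mg once daily and adds one bracketed instruction on toxicity: "Reduce to 300 mg/day if serious adverse effects develop". The row carries no exception and no pointer to other text. The adverse-reactions row of the same drug block classes myelosuppression as serious, together with "optic and peripheral neuropathy (increased risk with prolonged treatment and may be irreversible) lactic acidosis". The contraindications row lists hypersensitivity to the drug class and symptoms of neuropathy in the extremities.

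Appendix I, part 3, gives initial management by event:

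- Lactic acidosis, with linezolid as the likely drug: "Stop linezolid".
- Visual disturbance or optic neuritis, with likely drugs "Ethambutol / linezolid": "Stop suspect drug Seek ophthalmology support".
- Peripheral neuropathy: "Consider whether drug doses can be reduced without compromising the regimen", with switching of culprit drugs as a further option.
- Haematological abnormalities: consider reducing or suspending linezolid.

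Section 10.4 sends the reader to Appendix I for medical management. Appendix I describes itself as an addition to Section 10.4.

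**The concern.** Lactic acidosis and optic neuropathy are serious linezolid reactions by Table 9's own classification, so the dose row covers them as worded. A clinician who follows that row continues linezolid at half dose. A clinician who follows Appendix I stops it for lactic acidosis, and stops it for optic neuritis if linezolid is the suspect.

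The stake is participant safety. Table 9 itself warns that the neuropathy may not reverse. The dose row is also narrower than the protocol's background: Section 2.3.1 describes linezolid toxicity in the BPaL evidence as "manageable with dose reduction and interruption of linezolid use", and only the reduction has been carried into the row.

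**Working it through.** There is no figure to reproduce. The check sets the instructions for each serious linezolid reaction side by side.

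| Serious reaction (Table 9) | Table 9 dose row | Appendix I, part 3 | Same first action? |
|---|---|---|---|
| Lactic acidosis | 600 to 300 mg/day | Stop linezolid (0 mg/day) | No |
| Optic neuropathy | 600 to 300 mg/day | Stop the suspect drug, ethambutol or linezolid | No, if linezolid is the suspect |
| Myelosuppression | 600 to 300 mg/day | Consider reduction or suspension | Compatible |
| Peripheral neuropathy | 600 to 300 mg/day | Consider reduction; switching may be needed | Compatible between these two texts, but see step 4 |

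1. **Count.** Two of the four listed reactions have a different first action in Appendix I.

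2. **Strength of the two conflicts.** For lactic acidosis, Appendix I names linezolid and gives one action, so the conflict is direct. For optic neuritis it names two candidate drugs and leaves the attribution open. Table 2 includes a regimen with both, the South African short course: "SA: (4-6)BDQ-Lfx (or MXF)- LZD, INHhd-CFZ-E-Z/ (5) LFX-CFZ-E-Z". In that regimen the Appendix I row does not by itself tell the clinician to stop linezolid.

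3. **Is one text ranked above the other?** Section 10.4 points to Appendix I, and Appendix I supplements Section 10.4. Sections 8.1, 8.2, 10.1 and 12.2 cover interruption, discontinuation, clinician judgement and medical monitoring. None of them says that an Appendix I row overrides a Table 9 dose instruction, or the reverse.

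4. **The peripheral neuropathy entry.** The dose row and Appendix I both allow reduction. The linezolid contraindications row in Table 9, however, lists neuropathy symptoms in the extremities without saying whether that bars starting the drug or also continuing it. If it covers continuing, it does not agree with the reduction option in Appendix I.

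5. **Does the choice matter for treatment?** Under the pretomanid contraindications row of Table 9, permanently stopping linezolid in the first four weeks also ends the BPaL regimen. A later stop lets bedaquiline and pretomanid continue. A dose reduction triggers neither rule, so the two instructions can lead to different regimens.

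6. **How Table 9 treats other drugs.** The bedaquiline block states when to discontinue. The pretomanid block gives liver-function thresholds for interrupting the regimen, and these match the stop thresholds in the hepatotoxicity row of Appendix I. The linezolid block has no corresponding stop trigger for lactic acidosis or optic neuritis.

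**The case against.** The strongest reply is that the roles are already divided. Table 9 is a summary of drug profiles, its bracket supplies the reduced dose level, and Section 10.4 directs the reader to Appendix I for management. On that reading, a general line and a specific table are ordinary drafting, and harm requires a clinician who consults the dose row alone. This has force, and a careful clinician would probably follow the more specific row. It does not remove the conflict, because the bracket is worded as an action for serious effects and has no exception.

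The protocol also foresees stopping linezolid elsewhere. The pretomanid row sets out what follows if it is discontinued. Section 8.1 deals with linezolid doses missed because of adverse reactions. Section 8.2 allows permanent suspension for severe toxicity, and Section 10.1 leaves each decision to the attending clinician. A reader might infer that the protocol as a whole permits only reduction. These provisions show that it does not, and the point is confined to the dose row.

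For optic neuritis, the Appendix I table covers initial management and Section 8.1 allows gradual re-introduction once a reaction resolves. Stopping and then resuming at a lower dose would fit both texts. That stands as a reason to treat this conflict as the weaker one, although no passage sets out the sequence.

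A reader might also infer from Table 2 that most participants on linezolid receive no ethambutol, so that linezolid would nearly always be the optic neuritis suspect. The protocol does not support this. It gives no split of participants by regimen, and it does not list the components of the proposed bedaquiline-based regimen for RR-TB and MDR-TB. South Africa, whose current short course contains both drugs, supplies 440 of the 880 Cohort 1 participants. Counting regimens does not measure exposure.

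**Conclusion.** The inconsistency holds and is minor. The dose row and Appendix I give different first actions for lactic acidosis and, where linezolid is the suspect, for optic neuritis. The protocol does not say which governs. The point rests mainly on lactic acidosis.

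Clinician discretion, the interruption and suspension provisions, and the duty in Section 8.1 to discuss treatment changes with the medical monitoring team all reduce the practical risk.

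A reader might infer a consequence for the favourable-outcome endpoint, because a permanent change of at least two drugs for adverse reactions counts as treatment failure in Table 7. The documents do not support that step. They give no rate for either reaction, and nothing says that an initial stop would be permanent. The conclusion assumes only that the word serious in the dose row has the same meaning as in the adverse-reactions row of the same drug block.

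**What to change.** Replace the bracket in the Table 9 linezolid dose row with wording to this effect:

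> Stop linezolid for lactic acidosis or suspected linezolid-related optic neuritis. For myelosuppression, consider 300 mg/day or interruption. For peripheral neuropathy, follow Appendix I (reduce, interrupt or switch) with medical monitoring team review. See Appendix I.

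Reduction and switching already stand in the peripheral neuropathy row of Appendix I. Interruption appears in the note under its monitoring table.

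In the linezolid contraindications row, state whether neuropathy symptoms bar starting the drug only or also continuing it, so that the row agrees with Appendix I. Without this, the new dose wording would sit unreconciled beside the contraindication.

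The cost is a wording change to two rows of one table. Appendix I can stay as written, provided the contraindication is settled in line with it. No procedures, participants or data are added, and the sample size and analysis are unaffected.
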